## ETHICAL CONSIDERATIONS

The study has the approval of the Scientific Research Committee (CEIm) of the Fundació Unió Catalana d'Hospitals (See Appendix 3).

During the study, the international ethical standards for human research established in the principles defined in the Declaration of Helsinki and subsequent revisions (Fortaleza, Brazil, October 2013), the Code of Clinical Practices and national recommendations of in accordance with current legislation established in Law 14/2007 on Biomedical Research.

This study will be carried out in accordance with the principles established in the CIOMS International Guidelines. This study will guarantee respect for people through the universal ethical principles of beneficence, non-maleficence, and justice.

The protocol will be explained to the patient and information provided at all times; patients will be asked whether they want to be included, although this does not necessarily imply that patients themselves must sign the consent form. When patients are unable to sign, a family member or legal representative will be asked to sign. In this way, respect for the principle of autonomy is guaranteed. When the patient or the representative requests their withdrawal from the database despite having signed the consent, it will be withdrawn and the data will be deleted.

This study will be under the Spanish and European legislation: The Organic Law 3/2018, of December 5th on Protection of Personal Data and Guarantee of Digital Rights and Regulation (EU) 2016/679 of the European Parliament and of the Council, of April 27th, 2016, on the protection of natural persons in relation to the processing of personal data and the free circulation of these data ("General Data Protection Regulation" or "RGPD"), fully applicable as of May 25th, 2018.

### **SUMMARY**

Introduction: At present, the standard spontaneous breathing test (SBT) during weaning from mechanical ventilation is a 30-min test with pressure support 8 cmH2O without PEEP. There is a debate about the possible alveolar collapse during SBT and extubation. Our research group coordinates a RCT to compare standard strategy to a lung volume preservation strategy using PEEP and avoiding aspiration. Ultrasound is a non-invasive diagnostic and monitoring tool that allows assessment of lung aeration.

Hypothesis: A lung volume preservation strategy with 30-minutes SBT with PS 8cm H2O and 5cmH2O PEEP followed by extubation without suctioning correlates with a better ultrasound pattern of lung aeration.

Primary objective: Determine the difference in ultrasound lung aeration in two opposing weaning strategies (standard versus lung volume preservation strategy).

Secondary objectives: describe effect of PEEP, aspiration, diaphragm and intercostal musculature during SBT in each arm and in success or failure of SBT or extubation. Assess differences in derecruitment, and specifically in the postero-basal regions and its influence in extubation succeed, ICU stay, hospital stay and mortality.

Design: Nested substudy in the blinded randomized controlled prospective multicenter clinical trial: “Preserving lung volume at extubation. A prospective, randomized controlled multicenter trial” (NCT05526053) (CEI 22/67). The effect in the lung aeration pattern in a volume preservation strategy at extubation is compared to the standard strategy through a lung ultrasound score.

## INTRODUCTION

Mechanical ventilation is the main reason for Intensive Care Unit (ICU) admission.

Spontaneous or Self Breathing Test (SBT) is the most effective form in order to evaluate extubation. The latest guidelines (i) recommend using pressure support ventilation (PSV) and the latest Randomized Clinical Trial (RCT) (ii) shows that SBT of 30 minutes with 8cm H2O PSV yield higher rates of successful extubation compared to T-tube for 2 hours, mainly due to better test tolerance. However no differences in re-intubation, length of stay or mortality are observed in a 2020 systematic review (iii).

The causes currently related to extubation failure are multifactorial (iv, v, vi): airway or pulmonary dysfunction, increased resistance, decreased compliance, gas exchange alteration, central nervous system dysfunction and delirium, cardiac dysfunction, respiratory muscle function (mainly the diaphragm), weakness and fatigue, and endocrine dysfunction.

### FACTORS INFLUENCING DURING SBT AND EXTUBATION MANEUVER ON LOSS OF PULMONARY AERATION

- Diaphragm weakness

The diaphragm is the muscle that contributes the most to unassisted ventilation, but the mechanisms why diaphragmatic dysfunction is related to SBT failure remain unclear. They probably involve a combination of a decrease in diaphragm force and an increase in impedance that leads to a loss of lung aeration, alveolar collapse and atelectasis (vii).

- Decreased positive pressure

The decrease in inspiratory positive pressure favours collapse during inspiration, like PEEP withdrawal does during expiration and this increases the work of breathing for alveolar opening. An ongoing RCT (NCT 04939285) compares two strategies with PEEP and no PEEP.

- Secretions aspiration:

Aspiration favours collapse, while the maintenance of PEEP during cuff-deflation and endotracheal tube (ETT) removal according to an RCT (viii) allows the passage of air flow between the ETT and the larynx to improve the discharge of secretions.

[figure not shown]
## ASSESSMENT OF THE PULMONARY AERATION DEGREE

### - LUNG AND DIAPHRAGMATIC ULTRASOUND

The association between diaphragmatic dysfunction with appearance of pulmonary edema and a pattern of less aeration has been described. A meta-analysis (ix) describes some of the most outstanding parameters:

[figure not shown]
[figure not shown]

- Lung aeration level by Lung Ultrasound Score (LUS score). The latest international guidelines of 2022 (x) recommend exploring the maximum possible lung areas, but adapted to the clinical condition. This index recommends the exploration of 12 areas, 6 in each hemithorax (anterior, lateral and posterior subdivided into superior and inferior) [figure 1], giving a score of 0 to 3 points for each depending on the degree of regional aeration [figure 2]: N (normal aeration): presence of pleural sliding with A lines and less than 2 isolated B lines → 0 points; B1 (moderate loss of aeration): more than 2 well-defined B lines → 1 point; B2 (severe loss of aeration): multiple coalescing B lines → 2 points; C (consolidation): pattern of consolidation → 3 points. Ranging from 0 to 36 points, a score of <13 points at the end of a successful SBT is predictive of successful extubation (xi).

Figure 1. Lung Ultrasound Score scan areas.

Rouby, *Am J Respir Crit Care Med*, 2018.

Figure 2. Lung Ultrasound Score according to ultrasound pattern.

0	Normal aeration	Horizontal A-lines (or no more than two B-lines)	
1	Moderate loss of aeration	Multiple B-lines (either regularly spaced (7mm apart), or irregularly and even coalescent, but only visible in a limited area of the intercostal space)	
2	Severe loss of aeration	Multiple coalescent B-lines in prevalent areas of the intercostal spaces and observed in one or several intercostal spaces	
3	Complete loss of aeration	Lung consolidation with or without air bronchograms	

Tuinman, *Intensive Care Med*, 2020 (xii)

Simplified indices, such as the modified Lung Ultrasound Score (LUSm) (xiii) with exploration of 4 areas in critically patients have been used to avoid mobilization and consequent complications in ICU. LUSm has shown a relationship with the success or failure of extubation and good correlation between different observers. In this case, 4 areas are analysed: antero-superior, antero-inferior, lateral, and postero-basal [figures 3 and 4]. According what has been described in literature reviews, this last area is the place where most pathology is found in critical ill patients (xiv). The score range is between 0 and 24 points with risk of extubation failure described for values >7.

Figure 3. LUSm scan areas: 1-antero-superior, 2-antero-inferior, 3-lateral.

[figure not shown]
[figure not shown]

[figure not shown]
Figure 4. Postero-basal exploration area.

Lichtenstein, *Breathe*. 2017.

· Ultrasound assessment of the respiratory muscles (xv). Different measurements of the main muscle implied in breathing have been suggested such as the diaphragmatic thickening fraction (DTF) [figure 5], diaphragmatic excursion (DE) during the respiratory cycle that have been linked to successful extubation both as its own measure and related to the Rapid Shallow Breathing Index (RSBI) (xvi) or even loss of diaphragmatic thickness between the first 24-48 hours of mechanical ventilation and SBT (xvii, xviii).

Figure 5. Diaphragmatic thickening measurement.

[figure not shown]

Song, *BMC Pulmonary Medicine*, 2022.

A relationship between diaphragmatic atrophy and the influence on the inspiratory effort has also been described (xix).

In the evaluation of accessory muscles, its active use indicates high work of breathing and low diaphragmatic capacity. For this, the thickening of the intercostal musculature (Parasternal Intercostal Muscle Ultrasound) and its thickening fraction (TFic or InterCostal Thickening Fraction) as a measurement of respiratory effort has also been described. [figure 6].

Figure 6. Intercostal thickening measurement.

Dres, *Critical Care Medicine*, 2020.

In summary, part of the causes of extubation failure related to SBT and the ETT withdrawal manoeuvre are related to lung derecruitment or lung collapse, understood as the loss of aerated alveolar surface, partly caused by positive pressure withdrawal, secondary retraction and the lack of ability of the patients to preserve those correctly expanded areas.

Given the multiple factors involved in extubation failure, among the factors discussed, the importance of the recruitment status prior to SBT, the degree of loss during the test, peri-extubation, or the measures for the maintenance of post-extubation recruitment such as prophylactic non-invasive mechanical ventilation (NIV), high-flow nasal cannula therapy (HFNC) or the role of physiotherapy are unknown.

Lung ultrasound is a non-invasive diagnostic and monitoring tool that allows an assessment of the respiratory muscles and the degree of aeration that can be performed at different times in the SBT and extubation process.

Our research group leads and coordinates the RCT “Preserving Lung Volume at Extubation. A Prospective, Multicenter Clinical Trial” (NCT05526053) to compare two opposing extubation strategies: 1) on the one hand a standard 30-minute SBT with pressure support (PSV) modality of 8cmH2O without end-expiratory pressure (PEEP) followed by extubation with suction, versus 2) a lung volume preservation strategy with 30-min SBT with PSV 8cmH2O and PEEP 5cmH2O followed by extubation without

suction. This study was approved by the Ethics Committee of the *Fundació Unió Catalana d'Hospitals* (CEI 22/67) in August 2022.

The present substudy proposes the assessment of the respiratory muscles and the ultrasound pattern of lung aeration using LUSm at different times in the two opposite strategies in the process of SBT and extubation to assess their impact on derecruitment.

## **HYPOTHESIS**

The lung volume preservation strategy with 30-minutes SBT with PS 8cm H2O and 5cmH2O PEEP followed by extubation without suctioning correlates with a better ultrasound pattern of lung aeration.

## **OUTCOMES**

### **PRIMARY OUTCOME:**

Determine the difference in ultrasound lung aeration in two opposing weaning strategies (standard versus lung volume preservation strategy).

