## STATISTICAL ANALYSIS AND CALCULATION OF SAMPLE SIZE

Considering a basal extubation success of 82%, estimating an increase in absolute extubation success rate of 5%, with an alpha error of 0.05 and a power of 80%, requires a sample size of 822 patients in each group. With the participating hospitals, this sample will be obtained in 12 to 18 months, according to the recruitment rates. Recruitment will begin in October 2022 and will end in May 2024.

The randomization will be carried out with the built -in tool of the REDCAP® platform with computerized random numbers tables and patient N blocks for each hospital (researchers will be blinded on this data). Each participating center will have two different Redcap® profiles. The "recruiter" will have access only to the randomization tool and will not have access to data entry (only one recruiter per center). Another profile will be the "researcher" that will have access to randomization and data entry (as many profiles as researchers for each center). Researchers will have access to the data of their centers, but cannot access the data of other centers. Only trial coordinators will have access to data from all centers.

Before analyzing the results and managing the database, we will check the database to detect errors such as variables or repeated patients, or the lack of values in the

variables through the statistical computer program SPSS version 22® and R-Studio version 3.0®.

When half of the sample has been recruited, a preliminary analysis will be conducted to identify the trend of the results in the primary outcome. If significant ( $p < 0.005$ ) results have been obtained in one of the two randomization groups at that point, the inclusion of patients will be stopped. This analysis will be blinded to investigators.

In the descriptive analysis, quantitative variables will be expressed as means and standard deviations (if normally distributed) and as medians and interquartile ranges (if non-normally distributed). Qualitative variables will be expressed as frequencies and percentages.

Quantitative variables will be compared by Student's t-tests and qualitative variables by chi-square or Fisher's test.

Survival analyses for respiratory failure at 72 hours, reintubation at 72 hours, and mortality at 3 months will be performed with Kaplan-Meier curves with logarithmic rank test for comparison between both groups.

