### **SECONDARY OUTCOMES:**

- Describe the effect of PEEP during SBT on the ultrasound lung aeration pattern.
- Describe the effect of aspiration during extubation on the ultrasound lung aeration pattern.
- Describe the effect of the diaphragm (thickness, thickening fraction, and thickness evolution between admission and SBT) on the ultrasound lung aeration pattern.
- Describe the effect of the activity of the respiratory accessory muscles (parasternal thickness and thickening) on the pattern of lung aeration.
- Describe the pattern of ultrasound aeration, diaphragmatic thickness and accessory muscles in patients who fail extubation (1. Does not tolerate SBT and 2. Tolerates SBT and reintubation <72 hours).
- Describe the related variables to ultrasound lung aeration loss.

- Describe influence on aeration pattern of prophylactic HFNC or NIV and physiotherapy.
- Describe the ultrasound variables (lung aeration, diaphragm and accessory muscles) related to extubation failure. (1. Does not tolerate SBT and 2. Tolerates SBT and reintubation <72 hours.
- Describe and assess significant differences in the degree of ultrasound derecruitment (recruitment or  $\Delta$ RCT) in each strategy (standard and preservation of pulmonary volume)
- Describe and assess significant differences in ultrasound derecruitment ( $\Delta$ RCT) in patients who pass and those who do not pass SBT.
- Assess ultrasound de-recruitment ( $\Delta$ RCT) and correlate to ICU stay, hospital stay, extubation failure and mortality.

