#### SAMPLE SIZE

[figure not shown]
Considering significant a minimum difference of 1 point (SD 2,96) in the LUSm described by Tenza  (from 0 to 24 points) with an alpha error of 5 % and a power of 80 % 186 patients, 93 in each study group are required.

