## STUDY PROCEDURE

### IMAGE ACQUISITION MOMENTS

Images of the LUSm, diaphragm and intercostal musculature windows will be acquired following the scheme [figure 7], regardless of the standard or volume preservation arm.

Figure 7. Scheme of scan moments.

Essential scans:

1: pre-SBT LUSm

2: according to:

- If SBT fail: LUSm as early as possible, whether it can be before reconnection to ventilation or immediately after reconnection (to be specified).

- If SBT success: immediate post-extubation LUSm.

In case of failed SBT or failed extubation, patients do not re-enter the study.

It is recorded if rest has been performed after SBT, prophylactic high-flow oxygen therapy or non-invasive ventilation and respiratory physiotherapy have been indicated.

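### The ultrasound substudy's primary comparison names no scan time and no use of the pre-SBT LUSm, so precision that the collected data could give is not secured

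*Combined protocol and SAP*

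**What the plan says.** The substudy's Primary Outcome section reads "Determine the difference in ultrasound lung aeration in two opposing weaning strategies (standard versus lung volume preservation strategy". It gives no scan time, no reference to baseline and no estimator.

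The substudy's Sample Size section treats this as a plain two-group comparison of the score: "Considering significant a minimum difference of 1 point (SD 2,96) in the LUSm", with "alpha error of 5 % and a power of 80 % 186 patients, 93 in each study group are required". No before/after correlation appears in that text.

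Under Image Acquisition Moments, the pre-SBT LUSm is the first essential scan. The second depends on the SBT result: "If SBT success: immediate post-extubation LUSm", or "If SBT fail: LUSm as early as possible, whether it can be before reconnection to ventilation or immediately after reconnection". The LUSm acquisition section requires the same eight zones, depth and gain at each time. The Image Interpretation section has the images read by an observer blinded to strategy and to scan time.

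Change in aeration appears among the Secondary Outcomes: "Describe and assess significant differences in the degree of ultrasound derecruitment". It is labelled ΔRCT, and no formula is given.

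The substudy has no statistical analysis section. The main protocol's statistical section says: "Quantitative variables will be compared by Student's t-tests".

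**The concern.** The substudy asks whether one strategy preserves lung aeration, and its introduction gives the aim as assessing LUSm at different times to see the effect on derecruitment. Preservation is relative to what the patient had before the test. The design collects that starting value on the outcome's own scale, before the allocated SBT begins, but nothing in the primary outcome or the stated test uses it.

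Two things are at stake. If the pre-SBT score predicts the second score, an unadjusted comparison leaves that predictable variation in the error term and the interval is wider than it need be. A chance difference between arms in the pre-SBT score would also pass uncorrected into the estimate.

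There is a prespecification gap as well. The post score, the raw change and the baseline-adjusted difference all fit the present wording. They differ in precision, and the choice could be made after the data are seen.

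**Working it through.** **Inputs from the substudy's Sample Size section:** difference 1 point, SD 2.96, alpha 5% (taken as two-sided; not stated), 93 per arm, stated power 80%.

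**Assumed, not in the documents:** the correlation r between pre-SBT and second LUSm, shown over a range, and the same SD (2.96) at both scans.

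**1. The plan's own figure.** Unadjusted n per arm = 2 × 2.96² × (1.960 + 0.842)² / 1² = 137.5, so 138 (one-sided: 109). The stated 93 is not reproduced from the text inputs. At 93 per arm the unadjusted two-sided t-test has 63% power. This shortfall exists before any question of adjustment.

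**2. Formulas.**
- Post score alone: SD = 2.96
- Raw change: SD = 2.96 × √(2(1 − r))
- Baseline-adjusted (ANCOVA): SD = 2.96 × √(1 − r²)

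**3. Power at 93 per arm** (two-sample t-test, two-sided 5%; the normal approximation is at most about half a point higher):

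| r | ANCOVA SD | ANCOVA power | Change SD | Change power |
|---|---|---|---|---|
| 0 | 2.96 | 63% | 4.19 | 37% |
| 0.3 | 2.82 | 67% | 3.50 | 49% |
| 0.4 | 2.71 | 71% | 3.24 | 55% |
| 0.5 | 2.56 | 75% | 2.96 | 63% |
| 0.6 | 2.37 | 82% | 2.65 | 73% |
| 0.7 | 2.11 | 89% | 2.29 | 84% |

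The post score alone gives 63% in every row. Raw change is worse than the post score when r is below 0.5. ANCOVA is never worse than either, apart from one degree of freedom. Solving 137.5 × (1 − r²) = 93 gives r of about 0.57 as the correlation at which 93 per arm would reach 80%.

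**4. Precision without reference to power.** The unadjusted 95% half-width is 1.96 × 2.96 × √(2/93) = 0.85 point. At r = 0.5 it is 0.85 × √(1 − 0.25) = 0.74 point.

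**5. Chance imbalance.** With a baseline SD of 2.96, the arm difference in pre-SBT LUSm has standard error 2.96 × √(2/93) = 0.43. The chance of an absolute imbalance of at least 0.5 point is about 25% (0.5/0.434 = 1.15 standard errors, two-sided). That is half the target effect.

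**6. ΔRCT.** If ΔRCT is second score minus first, regressing it on arm and pre-SBT score gives the same arm coefficient as regressing the second score on arm and pre-SBT score. Subtracting the covariate from the outcome lowers only the covariate's own slope, by 1. A separate adjusted model for ΔRCT would add nothing.

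**The case against.** The strongest reply is that the plan is silent rather than wrong. No sentence says that the post-extubation score will be compared alone. The t-test comes from the main trial's analysis section, and the introduction's talk of different times leaves a before/after reading open. This stands. A reader might infer that the plan prescribes a post-only analysis, but the documents only point that way: the sample size is for a plain LUSm difference, ΔRCT is listed apart as secondary, and the one stated test has no covariate.

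A reader might also infer that omitting the baseline confounds the strategy effect with prior lung disease. The documents do not support that. Allocation is randomised, so the unadjusted comparison is unbiased, and only precision and chance imbalance are at stake.

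A third tempting inference is that missing adjustment causes the 63% power. It does not. With 138 per arm the unadjusted test would have about 80%, so the shortfall comes from the sample-size figure.

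The gain also depends on an unknown r. A high value is not assured, because the second scan is taken under different conditions from the first. At r = 0.3 the gain is about 4 points, and at r = 0 there is none.

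**Conclusion.** The point holds as a gap in specification with a cost in precision. The primary LUSm comparison has no stated scan time and no stated use of a baseline collected by design, and the only test on record is unadjusted. The result would still be valid, so this is an efficiency improvement and not a correction of bias.

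Under the plan's inputs and equal SDs, adjustment raises power at 93 per arm by about 4 points at r = 0.3, 12 at r = 0.5 and 26 at r = 0.7. The direction does not depend on r, but the size does. The mismatch between 93 and 138 per arm needs its own answer, and adjustment should not be presented as having settled it unless a value of r is justified. A figure in the Sample Size section was not readable and could hold further inputs. That bears on the mismatch, not on the wording of the primary outcome or the stated test.

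**What to change.** Add a short analysis paragraph to the substudy:

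- Define the primary analysis as the second-scan LUSm compared between randomised arms by linear regression with pre-SBT LUSm as covariate, reporting the adjusted mean difference with its 95% CI.
- Use the same model for the postero-basal sub-score, with its own pre-SBT value as covariate.
- Give the formula for ΔRCT. If it is second minus first, say that its arm comparison is the one from the primary model and drop any separate test.
- State how second scans after a failed SBT enter the analysis, since they are taken under other conditions than post-extubation scans. If they are left out, acknowledge that the comparison is then restricted by an outcome that arises after randomisation.
- State how a missing or unusable scan is handled.

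The cost is a few sentences, fixed before the data are compared by arm. No added scans, patients or data fields are needed. The failed-SBT rule is the only part that needs real discussion.
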